8.5.2.2.7 Biomarker

Per collection of whole blood, the following biomarkers will be analyzed (12 ml):

One Li-Heparin blood collection tube (5-6 ml):

Plasma equilibrium angiotensin levels:

Angiotensin II (Ang II)

Angiotensin 1-7 (Ang. 1-7)

Angiotensin 1-5 (Ang 1-5)

Angiotensin I (Ang I)

Angiotensin 1-9 (Ang 1-9)

Aldosterone

ACE2 Activity and ACE2 concentration

Cardiac pump function markers: NT-proBNP,
Ferritin

Other exploratory indicators: specific exploratory indicators will be determined as needed.

One EDTA blood collection tube (5-6 ml):

Plasma-Renin-Concentration (PRC)

Cytokines:

Interleukin- 6 (IL-6)

Interleukin- 8 (IL-8)

Soluble tumor necrosis factor receptor II (sTNFrII)

PAI-1

vWF

Tumor necrosis factor - α

Alveolar epithelial markers:

Soluble advanced glycation product receptor (sRAGE)

Surface-active protein-D (SP-D)

Endothelial markers:

Angiopoietin-2

Viral load

8.5.2.2.8 Electrocardiogram

A 12-lead ECG will be performed within 30 min after IMP administration (Table 1). Actual ECG assessment times will be monitored.

At a minimum, the date and time of when the event was performed, the investigator's assessment and the heart rate, RR, PR, QT, and QRS intervals are to be collected. All clinically significant abnormalities will be recorded on the appropriate source documents.

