1 STUDY SCHEME

2 STUDY SCHEDULES

Table 1:

Procedures and assessments	Screening period	Treatment period ²⁰							Follow up period		
	Day -1*	Day 1	Day 2	Day 3	Day 4	Day 5	Day 6	Day 7	Day 10 (±1 day) ¹⁶	Day 14 (± 1 day) ¹⁶	Day 28 End of Study Visit (or early termination visit) (± 1 day) ¹⁵
Informed consent	X										
Inclusion and exclusion criteria	X	X ※**									
Demographics ¹	X										
Medical history ²	X										
Randomization*		X ※*									
Treatment		X ¹⁴	X	X	X	X	X	X			
Score Assessment of WHO's 11-point scale	X	X ※**	X	X	X	X	X	X	X	X	X ¹⁹
PCR (quantitative or qualitative) ³	X	X ※**		X		X		X		X	X ¹⁷
Vital signs ⁴	X	X ※	X	X	X	X	X	X	X	X	X ^{17, 18, 19}
Physical examination ⁵	X	X ※**	X	X	X	X	X	X	X	X	X ^{17, 19}
Serum or urine pregnancy test ⁶	X										X ^{17, 19}
Clinical laboratory assessments ⁷	X	X ※**	X	X		X		X	X	X	X ^{17, 19}

	Screening period	Treatment period ²⁰							Follow up period		
Procedures and assessments	Day -1*	Day 1	Day 2	Day 3	Day 4	Day 5	Day 6	Day 7	Day 10 (±1 day) ¹⁶	Day 14 (± 1 day) ¹⁶	Day 28 End of Study Visit (or early termination visit) (± 1 day) ¹⁵
HIV/HBV/HCV Serology ⁸	X										
ECG ⁹	X	X ※**	X	X		X		X	X	X	X ^{17, 19}
Assessment of Respiratory condition ¹⁰	X	X ※**	X	X	X	X	X	X	X	X	X ¹⁷
mSOFA score	X	X ※**	X	X	X	X	X	X	X	X	X ¹⁷
Assessment of Immune function ¹¹		X ※**	X	X		X		X	X	X	X ^{17, 19}
Biomarker ¹²		X ※		X		X		X		X	X ^{17, 19}
Patient status assessment ¹³			X	X	X	X	X	X	X	X	X ¹⁷
Adverse Events		X	X	X	X	X	X	X	X	X	X
Concomitant Medication		X	X	X	X	X	X	X	X	X	X

* In case the required screening procedures take less time, randomization and start of treatment could be performed also on the same day then screening. The time period between start of screening procedures and start of treatment must not exceed 24 hours.

** Events do not need to be done if randomization is on the same day as Screening

※: prior dosing

mSOFA score: modified Sequential Organ Failure Estimated Score

¹ Demographic data: gender, age, ethnicity, height, history of allergies, history of smoking and alcohol use, weight, body mass index.

² Medical history: Medical history for the least 4 weeks.

³ If PCR was performed within 5 days before the screening visit, the test does not need to be repeated at screening and the available test results can be used.

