⁴ Vital signs include temperature, heart rate, respiration, blood pressure, and oxygen saturation. Vital signs need to be tested before and after each dose (within 30 min before/after IMP administration).

⁵ physical examination could also be documented in the context of the general visit/health status assessment e.g. during a general clinical review

⁶ Pregnancy Test: for FOCP only

⁷ Laboratory tests include the following: in case a local lab cannot perform any of these parameters it should be reported as missing value

- Inflammatory indicators: C- reactive protein (CRP), erythrocyte sedimentation rate (ESR), and procalcitonin.
- Blood routines include: red blood cell (RBC) count, hematocrit (HCT) or hematocrit total, and classification of white blood cells (WBC), hemoglobin (Hb), platelet (PLT) count.
- Urine routine includes: glucose (GLU), pH (PH), urinary protein (PRO), red blood cells (BLD), and white blood cells (LEU).
- Stool routine + occult blood: red blood cells (BLD), white blood cells (LEU), occult blood.
- Blood biochemistry includes: aspartate aminotransferase (AST), alanine aminotransferase (ALT), alkaline phosphatase (AKP), total bilirubin (TBI), total protein (ALB), albumin (ALB), urea nitrogen (BUN), Creatinine (Cr), uric acid (UA), potassium (K), sodium (Na), eGFR (assessment is calculated according to the formula used in local laboratory).
- Myocardial enzymes: creatine kinase (CK) and isoenzyme (CKMB), lactate dehydrogenase (of LDH), [alpha] - hydroxybutyrate dehydrogenase ([alpha] - HBD), troponin (of cTnI).
- Coagulation functions include: prothrombin time (PT), activated partial thromboplastin time (APTT), D- dimer, FIB

⁸ results do not need to be available before randomization, results up to 4 weeks old are acceptable

⁹ 12- lead ECG: within 30 min after IMP administration

¹⁰ Respiration: blood gas analysis (oxygenation index, blood lactic acid) or pulse oximetry.

¹¹ Immune function: immunoglobulin (Ig A, Ig M, Ig G)

¹² Biomarkers comprising (per collection of whole blood 10-12 ml)

1 Li-Heparin blood collection tube (5-6 ml):

1. Plasma equilibrium angiotensin levels: Angiotensin II (Ang II), Angiotensin 1-7 (Ang. 1 -7), Angiotensin 1-5 (Ang 1-5), Angiotensin I (Ang I), Angiotensin 1-9 (Ang 1-9)
2. Aldosterone
3. ACE2 Activity and ACE2 concentration
4. Other exploratory RAAS Biomarkers indicators: specific exploratory indicators will be determined as needed

1 EDTA blood collection tube (5-6 ml):

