1. Plasma-Renin-Concentration (PRC)
2. Cytokines: interleukin- 6 (IL-6), interleukin- 8 (IL-8), soluble tumor necrosis factor receptor II (sTNFrII), PAI-1, vWF, tumor necrosis factor - α
3. Alveolar epithelial markers: soluble advanced glycation product receptor (sRAGE), surface-active protein- D (SP-D)
4. endothelial markers: angiopoietin -2 (Angiopoietin-2)
- 5.
6. COVID-19 antibodies, viral load

¹³ Patient status assessments includes: no change, discharge from hospital, transition to critical illness, and death.

¹⁴ 1st dosing could also be on the evening of Day -1 in case randomization is on the same day as screening.

¹⁵ Follow-up Visits (Day 28) may be performed as phone visit or in-home visit where applicable. .

¹⁶ If a patient is already discharged from the hospital, the follow-up visits could be performed on an out-patient basis or at patient's home provided the patient agrees to that.

¹⁷ Assessments do not have to be performed in case of a phone visit

¹⁸ Targeted Physical examination by phone interview

¹⁹ The following assessments will be performed during in home-visits (Clinical Laboratory assessment, ECG, Assessment of immune function and Biomarker, if possible)

²⁰ If a patient will be discharged from hospital before day 7 treatment can be stopped at day of discharge.

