8.5.2.2 Study Examinations

Assessments are to be performed according to the schedule shown in Table 1.

On Day -1/1 of the study schedule the assessments have to be performed prior dosing.

Follow-up visit on Day 28 may be performed as a phone visit or in-home visit , where applicable . If a patient is already discharged from the hospital, the follow-up visits could be performed on an out-patient basis or at patient's home provided the patient agrees to that.

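### The Day 1 ECG is timed both before and after the dose, so the early ECG summaries can mix untreated and treated recordings

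*Protocol*

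**What the plan says.** **Pre-dose.** In Protocol Table 1 the Day 1 ECG cell carries the mark ※, which the table key defines as before dosing. Section 8.5.2.2 agrees: "On Day -1/1 of the study schedule the assessments have to be performed prior dosing". The same cell carries a double asterisk, explained as "Events do not need to be done if randomization is on the same day as Screening"; section 8.5.2.1 repeats that waiver.

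**Post-dose.** The label of the same ECG row carries footnote 9: "12- lead ECG: within 30 min after IMP administration". Section 8.5.2.2.8 says so again and cites the table: "A 12-lead ECG will be performed within 30 min after IMP administration (Table 1". It adds: "Actual ECG assessment times will be monitored", and lists date and time among the items to collect.

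**First dose.** Footnote 14 of Table 1 allows an early start: "1st dosing could also be on the evening of Day -1 in case randomization is on the same day as screening".

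**SAP.** Section 4 defines baseline as the latest value ahead of treatment. It equates this with the Day 1 value, and falls back on Screening when Day 1 is missing or is the same day. Sections 4 and 4.3 show a screening-day dose and its related assessments, with ECG named as an example, under the Screening label in tables, listings and graphs. Section 4.5 plans a frequency table of the ECG evaluation category and a listing of clinically significant abnormal ECGs. It makes no distinction by time relative to dose.

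**The concern.** One scheduled ECG has two timing rules, and a site that keeps one breaks the other. The conflict sits inside Table 1 (the cell mark against the row footnote) as well as between two text sections.

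ECG parameters are a named safety endpoint (Protocol 7.2.1, SAP 2.3), and SAP 4.5 lists cardiovascular effects among the important risks. A Day 1 count of abnormal ECGs is useful as an untreated reference or as a look at the first dose. If some recordings are one and some the other under a single label, it is neither. Sites that follow the pre-dose text would also have no scheduled ECG after a Day 1 first dose until Day 2.

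**Working it through.** The plan states no figure on this point and no arithmetic applies. The check sets the passages side by side.

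**Step 1. Could two ECGs be intended on Day 1?** Where the protocol wants paired measurements it says so: footnote 4 and section 8.5.2.2.3 require vital signs on both sides of every dose. The ECG text has no such wording, and Table 1 has one Day 1 cell. So one ECG is scheduled, with two rules.

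**Step 2. What does each rule produce?**

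| First dose | Pre-dose text followed | Post-dose text followed |
|---|---|---|
| On Day 1, screened the day before | Day 1 ECG is untreated; next scheduled ECG is Day 2 | Day 1 ECG is treated; the last untreated ECG is Screening |
| On the screening day (Day -1 evening) | Separate pre-dose Day 1 ECG waived; Screening ECG is untreated | ECG after that dose is shown under Screening, beside the untreated Screening ECGs; any ECG on Day 1 is already after the first dose |

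The first row shows how the Day 1 label can mix the two kinds of recording. The second row shows how the Screening label can, through the SAP's renaming rule.

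**Step 3. Does the SAP separate them?** Vital signs have their own rules in SAP 4.5: a Screening baseline and daily means over the before-dose and after-dose readings. ECG has no baseline rule of its own and no split by dose timing.

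**Step 4. Which outputs are exposed?** The described ECG outputs are the frequency table and the listing. No ECG change from baseline or shift table is described, although laboratory data and physical examinations have such analyses. The exposure is therefore the Screening and Day 1 part of the frequency summary.

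**Step 5. Which ECGs are safe?** Days 2, 3, 5 and 7 carry no pre-dose mark, so footnote 9 and section 8.5.2.2.8 apply without conflict. Days 10, 14 and 28 fall after treatment.

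**The case against.** **The specific mark overrides the general footnote.** Footnote 9 covers the whole row and cannot literally apply on Days 10, 14 and 28, when no study drug is given. It could be read as a general rule for dosing days, with ※ as the exception for Day 1. This reading is plausible, but it is written nowhere, and section 8.5.2.2.8 states the post-dose rule without qualification while citing Table 1. The passages still need reconciling.

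**The baseline is protected.** A reader might infer that the baseline ECG will be a treated one. The documents do not support that. The SAP's governing phrase requires a value ahead of treatment, a screening ECG is scheduled for everyone, and ECG times are recorded. No described ECG output uses a baseline in any case. What remains is that the SAP glosses baseline as the Day 1 value, so a programmer could go by visit label.

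**A Day 1 row is assumed.** SAP 4.5 says the laboratory summaries are by visit but does not say so for ECG. Layouts are in Appendix A, which is not in the text available. This stands: the mixing is possible under the plan as written, but not demonstrated.

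**The arms would be alike.** Center is a dynamic randomization factor (Protocol 8.1), so site habits should fall about equally on both arms. This stands: the harm is blurred interpretation, and bias between arms is unlikely.

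**The animal finding does not bear on the first dose.** A reader might link this gap to the ventricular ectopy in the monkey study (Protocol 6.5). That occurred in one animal on Day 12 of repeated dosing at the highest dose, 20.8 mg/kg/day, so it is no argument about a first-dose ECG.

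**Conclusion.** The contradiction is real and can be verified from the text. Its consequence is limited to how the early ECG frequency summaries can be read and, at sites that follow the pre-dose text, a possible absence of any ECG between the first dose and Day 2. It does not touch the primary endpoint, any hypothesis test, any described change-from-baseline ECG analysis, or the later on-treatment ECGs. Severity is low.

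The number of patients affected cannot be determined. A reader might take it to be all 200 planned patients. Same-day randomization waives the pre-dose Day 1 ECG, however, and the 200 includes an allowance of 200 − 186 = 14 for patients randomized but not treated (Protocol 8.7.2). A reader might also suppose that an acute effect in the Day 1 summary is diluted by half. That only restates an assumed even split of site practice, for which the documents give no basis.

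The conclusion assumes that sites could reasonably follow either text, and that the ECG table is laid out by visit without a timing split.

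**What to change.** 1. **Protocol.** The sponsor should reconcile the Day 1 ECG cell of Table 1, footnote 9, section 8.5.2.2 and section 8.5.2.2.8 so that they give one timing. Which timing is clinically right is for the sponsor.
2. **SAP 4.5.** Flag each ECG as before or after the first dose from its recorded date and time. Take any ECG baseline from the last recording before the first dose, whatever its visit label. Tabulate pre-dose and post-dose ECGs separately for Screening and Day 1, including ECGs that the renaming rule moves to Screening.

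The cost is a protocol clarification, a few SAP sentences and one derived variable. ECG times are already collected. The flag also needs the time of the first dose, which is assumed to be available in the study records. Because it works on recorded times, it can be applied to data already collected under either reading. It cannot recover a first-dose ECG that was never taken.

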8.5.2.2.9 Assessment of Respiratory Condition

To assess the respiration of the patient a blood gas analysis (oxygenation index, blood lactic acid) or pulse oximetry will be performed (Table 1).

Detailed information is provided in the Investigator Manual.

8.5.2.2.10 WHO 11-point scale

The WHO Clinical Progression Scale (WHO-CPS) measures patient illness by tracking progress through the healthcare system. The WHO-CPS incorporates a number of explicit features that are advantageous for its use in emerging infectious disease epidemic. It provides a measure of illness severity across an 11 point range from 0 (not infected) to 10 (dead) (Annex 1).

8.5.2.2.11 Modified Sequential Organ Failure Assessment (mSOFA) score

The mSOFA score [12] is made up of the following components:

- SpO₂/FiO₂ (mmHg)
- Central Nervous System: Glasgow coma score (GCS)
- Cardiovascular
- Liver
- Platelets
- Renal: Creatinine

Detailed information is provided in the Investigator Manual.

8.5.2.2.12 Patient status assessment

Patient status assessments includes the documentation of the following: no change, discharge from hospital, transition to critical illness, and death.

8.5.2.2.13 Adverse and Serious Adverse Events Assessments

The investigator is responsible for ensuring that all adverse events observed by the investigator or reported by patient are properly captured in the patients' medical records.

Adverse events will be recorded in the AE page of the eCRF using a recognized medical term or diagnosis that accurately reflects the event.

All AEs will be reviewed, confirmed, and classified (causality and seriousness) by a qualified, designated physician.

Pre-existing conditions that are present at screening are not defined as adverse events. These should be documented as medical history. Nevertheless, an AE will be documented in case of a worsening of severity of a pre-existing condition. AEs reported between screening and IMP application are defined as pre-treatment AE.

8.5.2.2.13.1 Definition of Adverse Events, Period of Observation, Recording of Adverse Events

An **AE** is any untoward medical occurrence in a clinical investigation patient administered a pharmaceutical product and that does not necessarily have a causal relationship with this treatment. An AE can therefore be any unfavorable and unintended sign (including an abnormal laboratory finding), symptom, disease or exacerbation of a pre-existing condition temporally associated with the use of a medicinal (test) product, whether or not considered related to the medicinal product (ICH Guidance E2A 1995).

All AEs, including those associated with the IMP, are collected from the time of first dose administration, regardless of the relationship to the IMP. All AEs are to be recorded on the appropriate source documents and subsequently will be entered into the AE module of the eCRF. All AEs have to be recorded until the last trial day according to the clinical trial protocol. If the investigator becomes aware of a serious AE considered related to the IMP, it has to be reported ([contact]) even if it occurs after finalization of the clinical trial.

All AEs must be followed to closure (i.e. the patient's health has returned to his/her baseline status or all variables have returned to normal), an outcome is reached, stabilization (the investigator does not expect any further improvement or worsening of the event), or the event is otherwise explained regardless of whether the patient is still participating in the clinical trial and clinical judgment indicates that further follow-up is not warranted. When appropriate, medical tests and examinations are performed so that resolution of event(s) can be documented.

Moreover, elective procedures (planned at time of randomization, e.g. catheter intervention of a coronary stenosis) will be determined as expected AE.

8.5.2.2.13.1.1 Severity Categorization

The severity of AEs must be recorded. If the severity of an AE/SAE changes, or if there are any other changes they must be made within the same AE record. Also, only the highest severity needs to be recorded. Worsening of pre-treatment events from the medical history, after initiation of IMP treatment, must be recorded as new AEs.

The medical assessment of severity is determined by using the following definitions:

Mild: Symptom barely noticeable to patient; does not influence performance or functioning. Prescription drug not ordinarily needed for relief of symptom but may be given because of personality of patient.

Moderate: Symptom of a sufficient severity to make patient uncomfortable; performance of daily activities influenced: patient is able to continue in clinical trial; treatment for symptoms may be needed.

Severe: Symptom causes severe discomfort. May be of such severity that patient cannot continue in clinical trial: Severity may cause cessation of treatment with test drug; treatment for symptom may be given and/or patient hospitalized.

The term "severe" is here used to describe the severity/intensity of the specific event; it is not the same as "serious", which is based on patient/event outcome or action criteria.

8.5.2.2.13.1.2 Relationship Categorization

An investigator assesses each AE for its relationship to the IMP.

The assessment of the relationship of an AE to the administration of IMP is a clinical decision based on all available information at the time of and after the occurrence of the event. The factors which may be considered when evaluating the relationship of an AE to the IMP include: time from exposure to IMP until onset of the event; recovery or improvement on discontinuation of IMP; availability of alternative explanations such as underlying or intercurrent diseases; concomitant medications or treatments; pharmacology of the IMPs; known response pattern for this class of drug; recurrence on reintroduction of the IMP.

If there is no reasonable possibility for suggesting a relationship, then the AE should be classified as ‘not related’. The adverse event should be classified as related if a reasonable possibility of a causal relationship between the event and IMP exists. This means that there are facts (evidence) or arguments to suggest a causal relationship. The causality must be documented in the source document and eCRF.

The following additional guidance may be helpful:

Term	Relationship	Definition
Related – Reasonable possibility	Yes	The temporal relationship between the event and the administration of the IMP is compelling and/or follows a known or suspected response pattern to that product, and the event cannot be explained by the patient’s medical condition, other therapies, or accident.
Not Related – No reasonable possibility	No	The event can be readily explained by other factors such as the patient’s underlying medical condition, concomitant therapy, or accident and no plausible temporal or biologic relationship exists between the IMP and the event.

8.5.2.2.13.1.3 Outcome Categorization

The outcome of AEs must be recorded during the course of the clinical trial in the eCRF. Outcomes are as follows:

- Recovered/Resolved
- Recovering/Resolving
- Not recovered/Not resolved/ongoing
- Recovered/Resolved with sequelae
- Fatal
- Unknown

8.5.2.2.13.1.4 Clinical Laboratory Evaluations

A change in the value of a safety laboratory investigation can represent an AE if the change is clinically relevant or if, during treatment with the IMP, a shift of a parameter is observed from a normal value to an abnormal value, or a further worsening of an already abnormal value. When evaluating such changes, the extent of deviation from the reference range, the duration until return to the reference range, either while continuing treatment or after the end of treatment with the IMP, and the range of variation of the respective parameter within its reference range, must be taken into consideration.

If, at the end of the treatment phase, there are abnormal laboratory values which were not present at baseline, further clinical or laboratory investigations should be performed until the values return to within reference range or until a plausible explanation (e.g., concomitant disease) is found for the pathological laboratory values.

Changes in laboratory values that are clinically significant (cs) and are specific for COVID-19 do not need to be documented as adverse events (AE). Clinically significant changes in laboratory values that are not due to COVID-19 need to be documented as AEs.

The physician should decide, based on the above criteria and the clinical condition of a patient, whether a change in a laboratory parameter is clinically significant and therefore represents an AE.

8.5.2.2.13.1.5 Overdose and Medication Error

Overdose, or medication error (as defined below) must be reported to the Sponsor according to the SAE reporting procedure whether or not they result in an AE/SAE.

Overdose - Intentional or unintentional administration of a dose of study medication higher than the protocol prescribed dose for each patient.

Medication Error - A mistake made in administration, and/or use of the study medication. For studies, medication errors are reportable only as defined below.

Administration of an expired product should be considered as a reportable medication error when associated with an AE, or if otherwise appropriate.

Cases of patients missing doses of study medication are not considered reportable as medication errors.

8.5.2.2.13.2 Serious Adverse Event (SAE) Procedures

8.5.2.2.13.2.1 Reporting Procedures

All initial SAE reports must be reported by the investigator to the Sponsor's Pharmacovigilance Department immediately, without undue delay, under no circumstances later than 24 hours following the first awareness of the event. All SAE follow-up reports must be reported in a timely manner. The investigator must complete, sign, and date the SAE form and verify the accuracy of the information recorded on the form with the corresponding source documents (Note: source documents are not to be sent unless requested) and e-mail the form to the Sponsor's Qualified Person for Pharmacovigilance:

Name: CTC North Safety Desk
[contact]
Email: [contact]

8.5.2.2.13.2.2 Serious Adverse Event Definition

A SAE is any untoward medical occurrence (whether considered to be related to IMP or not) that follows the first IMP administration at any dose:

- Results in death
- Is life-threatening

NOTE: The term 'life-threatening' in the definition of 'serious' refers to an event in which the patient was at risk of death at the time of the event; it does not refer to an event which hypothetically might have caused death if it was more severe.

- Requires inpatient hospitalization or prolongation of existing hospitalization
- Results in persistent or significant disability/incapacity
- Is a congenital abnormality/birth defect
- Is an Important Medical Event;

NOTE: Medical and scientific judgement should be exercised in deciding whether expedited reporting is appropriate in other situations, such as important medical events that may not be immediately life-threatening or result in death or hospitalization but may jeopardize the patient or may require intervention to prevent one of the other outcomes listed in the definition above. These should also usually be considered serious.

8.5.2.2.13.2.3 Pregnancy

Any report of pregnancy recorded for any female patient or for a female partner of a male patient should be reported to the Sponsor within the same timelines as an SAE, i.e. immediately (without undue delay, under no circumstances later than 24 hours following the first awareness/ within 30 days of IMP administration), but a separate form should be used. Pregnancy should be followed up at least until the birth or abort.

8.5.2.2.13.2.4 SAE Onset and SAE Stop Dates

The onset date of the SAE is defined as the date the event meets serious criteria. The stop date is the date the event no longer meets serious criteria, the date the symptoms resolve, or the event is considered chronic. In the case of hospitalizations, the hospital admission and discharge dates are considered the onset and SAE resolution dates, respectively.

8.5.2.2.13.2.5 Fatal Outcome

Any SAE that results in the patient's death (i.e. the SAE was noted as the primary cause of death) should have Outcome „Fatal” and the date of death recorded as the stop date of the SAE.

For all other events ongoing at time of death that did not contribute to the patient's death, the outcome should be considered unknown, with the SAE stop date (date of death) recorded.

For any SAE that results in the patient's death or any ongoing events at the time of death, the action taken with the IMP should be recorded as “dose not changed” or “not applicable” (if the patient never received IMP).

8.5.2.2.13.2.6 Regulatory Agency, Ethics Committee, and Investigative Site Reporting

The Sponsor is responsible for Suspected Unexpected Serious Adverse Reaction (SUSAR) reporting to the relevant Regulatory Authorities/European Union (EU), central Ethics Committees and investigators participating in the clinical trial in compliance with the legal reporting obligations.

The expedited reporting will occur not later than 15 days after the Sponsor has first knowledge of the adverse reactions. For fatal or life-threatening cases the term will be maximal 7 days for a preliminary report with another 8 days for completion of the report.

